#### **2.7.4.4 HF Signs and Symptoms**

- NYHA Classification (Class I: no limitation of physical activity; Class II: slight limitation of physical activity; Class III: marked limitation of physical activity; Class IV: unable to carry out any physical activity without discomfort).
- Paroxysmal nocturnal dyspnea (Absent, Present)
- Dyspnea at rest (Absent, Present)
- Dyspnea on effort (Absent, Present; if Present: Mild, Moderate, Severe)
- Fatigue (Absent, Present)
- Orthopnea (Absent, Present; if Present: 1 pillow (10cm elevation); 2 pillows (20 cm elevation); >2 pillows (>20 cms elevation))
- Jugular venous distention (Absent, Present, Not Available; if Present: <6 cm; 6 to 10 cm; >10 cm)
- Edema (Absent, Present; if Present: Trace; 1+; 2+; 3+; Feet and Ankles (no/yes); Lower legs of thighs (no/yes); Sacrum (no/yes))
- Rales (Absent, Present; if Present: Rales <1/3; Rales 1/3 to 2/3; Rales > 2/3)
- Third heart sound (Absent, Present, Not Available)

#### **2.7.4.5 Hospitalization**

Information related to hospitalization will be listed. The following will be presented:

- Type of hospitalization (Elective, Planned, Unplanned)
- Reason for hospitalization (refer to eCRF for list of reasons)
- Subject discharged (No, Yes, Unknown)
  - Duration of hospitalization in days [date of discharge – date of admission + 1]
- Subject admitted to ICU or Coronary Care Unit (CCU) (No, Yes, Unknown)
  - Number of days in ICU or CCU
- Discharge disposition (Home or with family/friends, Rehabilitation facility, Skilled nursing facility, Death, Unknown)

All hospitalizations (Cardiovascular (CV) Hospitalization, Non-Cardiovascular (non-CV Hospitalization and Undetermined Cause of Hospitalization)) will be adjudicated by the Events Adjudication Committee at Brigham and Women's Hospital.

Information on time from index hospitalization to randomization will be summarized.

#### **2.7.4.6 Angioedema**

Data collected from the Questionnaire for Angioedema-Like Event at Screening, Randomization and Follow-up visits will be summarized. Separate summaries will be produced for all angioedema events. The number and percentage for categorical variables and summary statistics for continuous variables of the following will be presented by visit, treatment group and open-label sacubitril/valsartan:

- Outcome (Not recovered/Not resolved, Recovered/Resolved, Recovering/Resolving, Recovered/Resolved with Sequelae, Fatal, Unknown)

- Duration of angioedema in days [*end date – start date + 1*]
- Timing of event (After first dose, after multiple doses, dose not given) [not asked at screening]
  - Study medication discontinued due to event (No, Yes, Unknown)
  - Event occurred within 1 day of dosing (Within 1 day of dose but less than or equal to 1 hour, within 1 day of dose but greater than 1 hour, After 1 day of dosing, Unknown)
- History of prior angioedema or angioedema like event (No, Yes, Unknown)
  - If yes, medications taken at time of previous event:
    - ACE inhibitor (No, Yes, Unknown)
    - ARB (No, Yes, Unknown)
    - Renin inhibitor (No, Yes, Unknown)
    - Other medications (No, Yes, Unknown)
- Presence of hereditary angioedema (No, Yes, Unknown)
- Any family members with history of angioedema-like events (No, Yes, Unknown)
- Signs and symptoms for current event
  - Shortness of breath/dyspnea (No, Yes, Unknown)
  - Difficulty swallowing/dysphagia (No, Yes, Unknown)
  - Difficulty speaking/dysarthria (No, Yes, Unknown)
  - Pain on swallowing/odynophagia (No, Yes, Unknown)
  - Stridor (No, Yes, Unknown)
  - Abdominal pain (No, Yes, Unknown)
  - Other (No, Yes, Unknown)
- Edema present (No, Yes)
  - Periorbital edema (No, Yes, Unknown)
  - Head edema (No, Yes, Unknown)
  - Neck edema (No, Yes, Unknown)
  - Lip edema (No, Yes, Unknown)
  - Tongue edema (No, Yes, Unknown)
  - Throat edema (No, Yes, Unknown)
  - Submandibular edema (No, Yes, Unknown)
  - Genitalia edema (No, Yes, Unknown)
  - Extremities edema (No, Yes, Unknown)
  - Other (No, Yes, Unknown)
- Previous edematous episodes (No, Yes, Unknown)
  - Number of previous edematous episodes
- ACEi taken in the past (No, Yes, Unknown)
- ACEi taken during trial participation after Screening (No, Yes, Unknown) [not asked at Screening]

- Dose changed within 2 days of event (No, Yes, Unknown)
- ARB taken in the past (No, Yes, Unknown)
- ARB taken during trial participation after screening (No, Yes, Unknown) [not asked at Screening]
  - Dose changed within 2 days of event (No, Yes, Unknown)
- Subject suffering from influenza, common cold or upper respiratory tract infection (No, Yes, Unknown)
- Medication allergies (No, Yes, Unknown)
- Food allergies (No, Yes, Unknown)
- Potential causes of angioedema-like event
  - Food (No, Yes, Unknown)
  - Insect bite (No, Yes, Unknown)
  - Animal exposure (No, Yes, Unknown)
  - Medication (No, Yes, Unknown)
  - Dental work (No, Yes, Unknown)
  - Pollen (No, Yes, Unknown)
  - Dust (No, Yes, Unknown)
  - Concomitant disease (No, Yes, Unknown)
  - Idiopathic (No, Yes, Unknown)
  - Other (No, Yes, Unknown)
- Medical intervention (No, Yes)
  - Administration of H-1 blocker (No, Yes)
  - Administration of H-2 blocker (No, Yes)
  - Administration of steroids (No, Yes)
  - Administration of epinephrine (No, Yes)
  - Admission to hospital (No, Yes)
  - Admission to the emergency room (No, Yes)
  - Endotracheal intubation (No, Yes)
  - Tracheostomy (No, Yes)
  - Discontinuation of ACE inhibitor (No, Yes)
  - Discontinuation of ARB (No, Yes)
  - Other

All assessment data will be listed as collected in the CRF.

## 2.8 Pharmacokinetic endpoints

Not applicable.

## **2.9 Pharmacodynamic and pharmacokinetic/pharmacodynamic analyses**

Not applicable.

## **2.11 Biomarkers**

NT-proBNP will be collected and descriptively summarized by visit, treatment group. NT-proBNP will be measured in all subjects using the central laboratory at Visits 2 (randomization), 3, 5, and 7 (Weeks 0, 1, 4, and 8 respectively). Values and the change from Baseline for each parameter will be summarized by visit and treatment group. Analyses will be based on the FAS.

NT-proBNP values will be based on clinical laboratory samples processed and assessed by the central laboratory.

[figure not shown]

P  
D

Additional analysis of biomarkers is discussed in Protocol [Sections 2.5, 2.7, and 2.13](#).

Biomarker samples from subjects who withdrew consent will not be analyzed by the central laboratory.

## **2.13 Interim analysis**

There is no planned interim analysis for efficacy in the study.

### *Interim Safety Assessment*

An independent DMC will be responsible for performing interim safety assessment using independent statistician and programmer who will not be involved in the trial conduct. The DMC charter will contain the committee's responsibilities regarding the interim safety assessment. Details of this safety assessment will be included in the DMC-SAP.

Interim safety assessments are planned to be performed and results will be provided to DMC for their review and recommendation. There are 3 DMC planned and the timing of these safety

assessments are mentioned in the DMC Charter. No adjustment to the level of significance will be made for these interim safety assessments.

### **3 Sample size calculation**

The target sample size for this study is approximately 450 total subjects (including original protocol and all Amendment subjects), randomized into the 2 treatment groups in a 1:1 ratio. The maximum planned duration of follow-up after randomization of these subjects is approximately 20 months and the planned duration of follow-up for the last subject in the group is 2 months.

The power of the study is determined based on these 450 subjects for the primary endpoint.

#### **Sample size for the primary endpoint**

This sample size of 450 subjects would have 85% power to detect a 23% reduction in the geometric mean of the proportional change from Baseline to an average of Weeks 4 and 8 in NT-proBNP for the sacubitril/valsartan treatment group. This 23% reduction in geometric mean is equivalent to -0.2614 in natural log scale ( $=\ln(0.77)$ ). The power is estimated assuming a two sided significance level of 0.05, a common SD of 0.85 for change in log transformed NT-proBNP and a 15% rate of missingness in NT-proBNP at baseline or at both Week 4 and Week 8.

nQuery Version 8.4.1.0 (2019) software package is used in calculating the power of the test.

### **4 Change to protocol specified analyses**

## **5 Appendix A**

### **5.1 Imputation rules**

#### **5.1.1 Study drug**

Full dates for study treatment collected on the eCRF are required; therefore, no imputations will be made.

#### **5.1.2 AE date imputation**

The following algorithm should be used to estimate start dates for which only partial information is known:

- Missing day and month

- If the year is the same as the year of first study treatment, then the day and month of the start date of treatment will be assigned to the missing fields.
- If the year is prior to the year of first study treatment, then December 31 will be assigned to the missing fields.
- If the year is after the year of first study treatment, then January 1 will be assigned to the missing fields.
- Missing month only
  - Treat day as missing and replace both month and day according to the above procedure.
- Missing day only
  - If the month and year are the same as the year and month of first study treatment, then the start date of treatment will be assigned to the missing day.
  - If the month and year are before the year and month of first study treatment, then the last day of the month will be assigned to the missing day.
  - If the month and year are after the year and month of first study treatment, then the first day of the month will be assigned to the missing day.

If the imputed start date result is after the stop date (and the stop date is complete), the imputed start date will be reset to the stop date.

The following algorithm should be used to estimate stop dates for which only partial information is known:

- Missing year
  - Date left missing.
- Missing month
  - Impute 'December'.
- Missing day
  - Impute 'last date of that month'.

### **5.1.3 Concomitant medication date imputation**

The following algorithm should be used to estimate start dates for which only partial information is known:

- Missing day and month
  - If the year is the same as the year of first study treatment, then the day and month of the start date of treatment will be assigned to the missing fields.
  - If the year is prior to the year of first study treatment, then December 31 will be assigned to the missing fields.
  - If the year is after the year of first study treatment, then January 1 will be assigned to the missing fields.

- Missing month only
  - Treat day as missing and replace both month and day according to the above procedure.
- Missing day only
  - If the month and year are the same as the year and month of first study treatment, then the start date of treatment will be assigned to the missing day.
  - If the month and year are before the year and month of first study treatment, then the last day of the month will be assigned to the missing day.
  - If the month and year are after the year and month of first study treatment, then the first day of the month will be assigned to the missing day.

If the imputed start date result is after the stop date (and the stop date is complete), the imputed start date will be reset to the stop date.

The following algorithm should be used to estimate stop dates for which only partial information is known:

- Missing year
  - Date left missing. Consider the medication to have been received at all periods after that period determined by the start date.
- Missing month
  - Impute ‘December’.
- Missing day
  - Impute ‘last date of that month’.

#### **5.1.3.1 Prior therapies date imputation**

The same imputation as concomitant medication will be used. See [Section 5.1.3](#).

#### **5.1.3.2 Post therapies date imputation**

The same imputation as concomitant medication will be used. See [Section 5.1.3](#).

#### **5.1.3.3 Other imputations**

Not applicable

### **5.2 AEs coding/grading**

The United BioSource Company, UBC coding team will code the AE terms using MedDRA terminology (v19.0 or later). If any terms are not coded, the data management team will issue queries to sites to update the AE term appropriately.

## 5.3 Laboratory parameters derivations

### 5.3.1 Laboratory grading

The collected laboratory values will be summarized by severity (low/normal/high) and not converted to Common Terminology Criteria for Adverse Events grades.

### 5.3.2 Notable laboratory values

Clinically notable laboratory abnormalities for selected tests based on a percent change from Baseline:

#### Hematology

RBC count	>50% increase, >20% decrease
Hemoglobin	>50% increase, >20% decrease
Hematocrit	>50% increase, >20% decrease
WBC count	>50% increase, >50% decrease
Platelet count	>75% increase, >50% decrease

#### Blood Chemistry

ALT (SGPT)	>150% increase
AST (SGOT)	>150% increase
BUN	>50% increase
Creatinine	>50% increase
Total bilirubin	>100% increase
CPK	>300% increase
Alkaline phosphatase	>100% increase
Potassium	>20% increase, >20% decrease
Chloride	>10% increase, >10% decrease
Calcium	>10% increase, >10% decrease
Uric acid	>50% increase

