	
6. Has not taken an ACEi for 36 hours prior to randomization

Key Exclusion criteria	
1) Any clinical event within the 90 days prior to randomization that could have reduced the LVEF (i.e., MI, CABG), unless an echo measurement was performed after the event confirming the LVEF to be >40%2) Entresto™ (sacubitril/valsartan) usage within the past 60 days3) eGFR < 20ml/min/1.73 m² as measured by the simplified Modification of Diet in Renal Disease (MDRD) formula at most recent assessment prior to randomization and within 24 hours prior to inpatient randomization or 72 hours prior to outpatient randomization4) Serum potassium > 5.2 mEq/L at most recent assessment prior to randomization and within 24 hours prior to inpatient randomization or 72 hours prior to outpatient randomization5) Acute coronary syndrome, stroke, transient ischemic attack; cardiac, carotid or other major CV surgery; percutaneous coronary intervention (PCI) or carotid angioplasty, within 30 days prior to randomization6) Probable alternative diagnoses that in the opinion of the investigator could account for the patient's HF symptoms (i.e. dyspnea, fatigue) such as significant pulmonary disease (including primary pulmonary HTN), anemia or obesity.7) Isolated right HF in the absence of left-sided structural heart disease8) History of hypersensitivity (i.e. including angioedema), known or suspected contraindications, or intolerance to any of the study drugs including ARNIs (i.e. sacubitril/valsartan), and/or ARBs9) Patients with a known history of angioedema due to any etiology10) Patients with a history of heart transplant or LVAD, currently on the transplant list, or with planned intent to implant LVAD or CRT device within the initial three months of enrollment during the trial11) A cardiac or non-cardiac medical condition other than HF with an estimated life expectancy of < 6 months12) Known pericardial constriction, genetic hypertrophic cardiomyopathy, or infiltrative cardiomyopathy including suspected or confirmed amyloid heart disease (amyloidosis)13) Life-threatening or uncontrolled dysrhythmia, including symptomatic or sustained ventricular tachycardia and atrial fibrillation or flutter with a resting ventricular rate >110 bpm14) Clinically significant congenital heart disease felt to be the cause of the patient's symptoms and signs of HF15) Coronary or carotid artery disease or valvular heart disease likely to require surgical or percutaneous intervention within the duration of the trial16) Any surgical or medical condition, which in the opinion of the investigator, may place the patient at higher risk from his/her participation in the study, or is likely to prevent the patient from complying with the requirements of the study or completing the study17) Known hepatic impairment (as evidenced by total bilirubin > 3 mg/dL, or increased ammonia levels, if performed), or history of cirrhosis with evidence of portal hypertension such as varices

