8.4.1 Laboratory evaluations

The local hospital and/or clinic laboratory will be used for all laboratory evaluations required to determine eligibility. If eligibility laboratory assessments were not done during the patient's hospitalization, samples should be collected and sent to the local laboratory. A central laboratory will be used for analysis of all collected specimens from baseline through the final visit. Details on the collections, shipment of samples and reporting of results by the central laboratory will be provided to investigators in the laboratory manual. Results from the local hospital laboratory will be recorded in the eCRF.

Clinically notable laboratory findings are defined in [Appendix 1](#).

Local laboratory assessments may be performed on an as-needed basis for unscheduled visits. Laboratory values that exceed the boundaries of a notable laboratory abnormality must be commented on by the investigator on the source document and additional laboratory evaluations should be performed, as judged appropriate by the investigator. If the laboratory abnormality induces clinical signs or symptoms, or requires therapeutic intervention, then the diagnosis or medical condition must be entered on the patient's AE eCRF. If the laboratory abnormality is the primary reason for an unforeseen hospitalization or otherwise fulfills the seriousness category of an AE, then the procedure for rapid notification of SAEs must be followed. Likewise, if the laboratory abnormality leads to discontinuation from the study drug (temporarily or permanently), the patient must be followed until the abnormality resolves or until it is judged to be permanent. This investigation may include continued monitoring by repeat laboratory testing or by performing additional laboratory tests as deemed necessary by the investigator or the Novartis medical monitor.

Table 8-3 Laboratory Assessments

Test Category	Test Name
Hematology	Hemoglobin, hematocrit, red blood cell count, white blood cell count with differential (Basophils, Eosinophils, Lymphocytes, Monocytes, Neutrophils, Bands, Other (absolute value preferred , %s are acceptable), and platelet count will be measured at Visits 1 (local lab), 2, 7, 11, 13, 15, 16, and 17 (central lab). Hemoglobin A1c will be measured at Visits 2 and 17 (central lab).

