16.1 Appendix 1: Clinically notable laboratory values and vital signs

Clinically notable laboratory abnormalities for selected tests based on a percent change from baseline:

Hematology

RBC count	>50% increase, >20% decrease
Hemoglobin	>50% increase, >20% decrease
Hematocrit	>50% increase, >20% decrease
WBC count	>50% increase, >50% decrease
Platelet count	>75% increase, >50% decrease

Blood Chemistry

ALT (SGPT)	>150% increase
AST (SGOT)	>150% increase
BUN	>50% increase
Creatinine	>50% increase
Total bilirubin	>100% increase
CPK	>300% increase
Alkaline phosphatase	>100% increase
Potassium	>20% increase, >20% decrease
Chloride	>10% increase, >10% decrease
Calcium	>10% increase, >10% decrease
Uric acid	>50% increase

16.2 Appendix 2: Treatment guidelines for hyperkalemia (serum potassium greater than or equal to 5.5 mEq/L)

General principles

Elevation of potassium levels above the predefined values should be repeated and confirmed before any action is taken.

Any patient who experiences a potassium level ≥ 5.5 mEq/L confirmed by repeated testing after randomization requires regular, repeated checks of potassium concentration (beyond that prescribed in the protocol) until it is clear that the potassium concentration is stable and not rising into the range of concern (≥ 5.5 mEq/L).

Patients with elevated potassium value will be managed according to the corrective actions outlined below and the investigator's clinical judgement. Hyperkalemia should be followed until resolution.

Recommended corrective action for management of hyperkalemia

Serum potassium > 5.3 and less than or equal to 5.5 mEq/L

- Confirm potassium concentration in a non-hemolyzed sample
- Reinforce low potassium diet and restriction of food/drinks with high potassium content (e.g. orange juice, melon, bananas, low-salt substitutes etc.)
- Review medical regimen (including dietary supplements and over-the-counter medications) for agents known to cause hyperkalemia. Consider reduction in dose or discontinuation of these agents:
- Aldosterone antagonists (if they are believed to be the most likely cause of hyperkalemia)
- Potassium-sparing diuretics (e.g. amiloride and triamterene) including in combination products with thiazide or loop diuretics
- Potassium supplements, e.g., potassium chloride
- Salt substitutes
- Non-steroidal anti-inflammatory drugs (NSAIDs)
- Cyclo-oxygenase-2 (COX-2) inhibitors

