- Trimethoprim and trimethoprim-containing combination products, such as Bactrim® and Septra® (trimethoprim/sulfamethoxazole fixed combination)
- Herbal Supplements:
 - For example, Noni juice, alfalfa (*Medicago sativa*), dandelion (*Taraxacum officinale*), horsetail (*Equisetum arvense*), nettle (*Urtica dioica*), milkweed, lily of the valley, Siberian ginseng, hawthorn berries
 - Repeat serum potassium measurement within 3 to 5 days
 - If serum potassium remains > 5.3 and ≤ 5.5 mEq/L, regularly monitor serum potassium levels to ensure stability (suggested once monthly)

- Consider down-titration of study medication, according to investigator's medical judgment.

Serum potassium > 5.5 and < 6.0 mEq/L

- Confirm potassium concentration in a non-hemolyzed sample
- Consider down-titration or temporarily discontinue study drug according to investigator medical judgment.
- Apply all measures outlined for serum potassium > 5.3 and \leq 5.5 mEq/L
- Repeat serum potassium measurement after 2-3 days
- If serum potassium < 5.5 mEq/L, consider resumption of study drug at lower dose with repeat potassium within 5 days

Serum potassium greater than or equal to 6.0 mEq/L

- Immediately discontinue study drug
- Confirm potassium concentration in a non-hemolyzed sample
- Urgently evaluate patient and treat hyperkalemia as clinically indicated
- Apply all measures outlined for serum potassium > 5.3 and < 6.0 mEq/L
- If serum potassium < 5.5 mEq/L, consider resumption of study drug at lower dose with repeat potassium within 5 days

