### **2.6.2.7 Analysis of secondary endpoint 7**

Incidence of below adverse events of special interest (AESI) during treatment will be considered.

- Incidence of symptomatic hypotension (Collected in AESI CRF)
- Incidence of hyperkalemia (potassium >5.5 mEq/L) (Collected in AESI CRF)
- Incidence of angioedema (Collected in AESI CRF)
- Incidence of worsening renal function, defined as an increase in serum creatinine of  $\geq 0.5\text{mg/dl}$  and worsening of the eGFR by at least 25% [using Central Lab data from same scheduled or unscheduled visits]

Incidence of adverse events of special interest (AESIs) will be analyzed using a logistic regression model with treatment and in-hospital/out-of-hospital randomization as fixed factors. The model will be used to estimate the odds ratio for treatment and its 95% CIs.

- The number (and proportion) of subjects with AESI will be summarized by treatment.
- The primary analysis of secondary endpoint 7 will be repeated but data that occurs after diagnosis as COVID-19 positive will be censored at the subject level.

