### 5.3.3 Clinically notable changes in vital signs

Vital Sign (unit)	Clinically notable criteria
Weight (kg)	decrease > 7% from Baseline increase > 7% from Baseline
Sitting systolic blood pressure (mmHg)	<90 and decrease from baseline of >20 >180 and increase from baseline of >20

Sitting diastolic blood pressure (mmHg)	<50 and decrease from baseline of >15 >105 and increase from baseline of >15
Pulse (bpm)	<50 and decrease from baseline of > 15 >120 and increase from baseline of >15

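### The notable-value rules for potassium and systolic pressure are least sensitive in patients who enter closest to the limit, and the SAP specifies no programmed count at the absolute levels to make up for it

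*SAP*

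**What the plan says.** **Laboratory rule.** SAP 5.3.2 introduces its list as "Clinically notable laboratory abnormalities for selected tests based on a percent change from Baseline". The potassium row reads ">20% increase, >20% decrease", with no absolute limit. Protocol Appendix 1 has the same row.

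**Blood pressure rule.** SAP 5.3.3 marks low sitting systolic pressure as notable when it is "<90 and decrease from baseline of >20". Both parts must be met.

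**Entry limits.** A patient is excluded for "Serum potassium > 5.2 mEq/L at most recent assessment prior to randomization". Systolic pressure must have been at least 100 mmHg for the 6 hours before randomization (Protocol 5.1).

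**Use of the rules.** SAP 2.1.1 provides for summaries of notable vital signs and laboratory abnormalities by study phase. SAP 2.7.3 flags notable laboratory values and SAP 2.7.4.2 tabulates notable vital signs. In the protocol, section 10.1.1 refers to Appendix 1 for alert ranges, and section 8.4.1 states: "Laboratory values that exceed the boundaries of a notable laboratory abnormality must be commented on by the investigator on the source document". The same sentence of 8.4.1 calls for further laboratory evaluation as the investigator judges appropriate.

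**Absolute levels elsewhere.** Protocol Appendix 2 has its own potassium bands. The lowest is "Serum potassium > 5.3 and less than or equal to 5.5 mEq/L". The highest starts at 6.0 mEq/L and carries the instruction "Immediately discontinue study drug". SAP 2.6.2.7 analyses "Incidence of hyperkalemia (potassium >5.5 mEq/L) (Collected in AESI CRF") by arm, together with symptomatic hypotension, also from the AESI form.

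**The concern.** Hyperkalemia and hypotension are both named among the trial's safety outcomes. A flag that depends on change from baseline asks most of the patients with the least room to move: a high entry potassium raises the value needed for a flag, and a low entry pressure lowers it. These are the patients in whom a reader of the safety tables would most want to see excursions. For pressure, they lie within the group below 110 mmHg that the SAP itself defines as a subgroup (SAP 2.2.1, item 6).

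What is at stake is the completeness of the descriptive safety tables and of one investigator-comment trigger in the protocol. The primary endpoint, its power and the secondary efficacy analyses are not affected.

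**Working it through.** The plan states no figure for this point, so there is nothing to reproduce first. The check is threshold algebra on the documents' own limits, followed by an illustration that needs assumptions.

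**1. Potassium (no assumption needed).** The upward flag fires when the value exceeds 1.20 × baseline. It coincides with 5.5 mEq/L at a baseline of 5.5 / 1.20 = 4.58. Above that baseline, some values over 5.5 are not flagged.

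| Baseline (mEq/L) | Flag needs a value above | Over 5.5 but unflagged |
|---|---|---|
| 4.8 | 1.20 × 4.8 = 5.76 | over 5.5, up to 5.76 |
| 5.0 | 1.20 × 5.0 = 6.00 | over 5.5, up to 6.00 |
| 5.2 | 1.20 × 5.2 = 6.24 | over 5.5, up to 6.24 |

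Two examples. A rise from 5.1 to 6.1 is 6.1 / 5.1 = 1.196, or +19.6%: not notable, although 6.1 is in the highest Appendix 2 band. A rise from 3.5 to 4.3 is 4.3 / 3.5 = 1.229, or +22.9%: notable.

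The limit of 5.2 applies to the eligibility sample, which goes to the local laboratory (Protocol 8.4.1). Analysis baseline is the last value before first dose (SAP 2.1.1), which can come from the central laboratory. A baseline above 5.2 is therefore possible and would widen the gap.

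**2. Systolic pressure (no assumption needed).** The low flag fires when the reading is below the smaller of 90 and baseline minus 20.

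| Baseline (mmHg) | Flag needs a reading below | Below 90 but unflagged |
|---|---|---|
| 100 | 80 | 80 to 89 |
| 105 | 85 | 85 to 89 |
| 109 | 89 | 89 |
| 110 or more | 90 | none |

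**3. How often (assumed distributions, illustration only).** The documents give no potassium distribution. Two sets of bivariate-normal simulations were run, with baseline cut at 5.2.

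- Narrow set: baseline mean 4.1 to 4.3, SD 0.40 to 0.45; follow-up mean 4.4 to 4.6, SD 0.5; correlation 0.4 to 0.5. Of values above 5.5, 25% to 47% are unflagged. Of values at 6.0 or more, 5% to 13% are unflagged. Of upward flags, 89% to 94% are at or below 5.5 and 55% to 67% at or below 5.0.
- Wide set: baseline mean 4.0 to 4.4, SD 0.40 to 0.50; mean rise 0 to 0.3; correlation 0.3 to 0.5. Of values above 5.5, 23% to 75% are unflagged. Of upward flags, 84% to over 99% are at or below 5.5 and 46% to 97% at or below 5.0. Values of 6.0 or more are too rare in several of these settings for a stable share.

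The direction holds throughout; the size does not settle.

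**4. What else counts these values.**

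| Planned output | Covers | Does not cover |
|---|---|---|
| AESI hyperkalemia, SAP 2.6.2.7 | above 5.5, odds ratio by arm | central values not entered on the AESI form |
| Hyperkalemia laboratory summary, SAP 2.7.3 | highest value for the event, re-tests | appears to depend on a recorded event |
| Shift tables, SAP 2.7.3 | low/normal/high to worst value | cannot separate above 5.5 or 6.0 and over from slightly high |
| AESI hypotension and its lowest pressure, SAP 2.6.2.7 and 2.7.4.2 | symptomatic episodes | low readings without symptoms |
| Vital signs by visit, SAP 2.7.4.2 | descriptive statistics by arm | number of patients below 90 |

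Within the same endpoint, worsening renal function is taken from central-laboratory data, so a programmed potassium count would follow a practice the SAP already uses.

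**The case against.** The strongest reply is that neither harm depends on the notable flag. Potassium above 5.5 belongs to secondary endpoint 7, with an odds ratio by arm (SAP 2.6.2.7). SAP 2.1.1 lists it for summary by study phase, separately from notable laboratory abnormalities. SAP 2.7.1.5 adds adverse-event summaries for hyperkalemia, and SAP 2.7.3 adds laboratory summaries, shift tables and a listing. The systolic rule does contain an absolute limit, and its gap closes at a baseline of 110. All of this stands, and it rules out several stronger readings that a reader might draw:

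- *That the plan hides a difference in hyperkalemia between arms.* It does not; that comparison is made elsewhere on the absolute scale. What remains is its source, the AESI form.
- *That flagged potassium rises are mostly harmless or normal.* The documents give no distribution or reference range, and Appendix 2 already acts above 5.3. The most that can be said is that, under the assumed distributions, most flagged rises are at or below 5.5.
- *That low pressure without symptoms appears nowhere else.* Visit statistics and listings include it, and it may be reported as an adverse event. What is missing is another planned count of patients below 90.
- *That Appendix 1 overrides Appendix 2 in managing patients.* Nothing makes Appendix 2 action conditional on an Appendix 1 flag, and Protocol 10.1.1 also directs review of values outside normal ranges. The mismatch concerns the alert and comment trigger: a value in the highest Appendix 2 band can lie inside the Appendix 1 limits.

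**Conclusion.** The point holds as a limited gap in safety reporting. The thresholds are exact. Potassium values above 5.5 can go unflagged at baselines over 4.58 mEq/L, up to 6.24 at a baseline of 5.2. Systolic readings from baseline minus 20 up to 89 go unflagged at baselines of 100 to 109 mmHg. How many patients this touches is unknown; the simulated shares (23% to 75% of values above 5.5 unflagged over the wider range) rest wholly on assumed distributions and should be read as illustration.

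After allowing for the other analyses, three gaps remain: the hyperkalemia count depends on form entry; no programmed count of central potassium above 5.5 or at 6.0 and over is planned; and the only planned threshold count of low systolic readings regardless of symptoms undercounts patients who enter at 100 to 109. No efficacy inference changes.

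**What to change.** **SAP 5.3.2 and 5.3.3.** Keep the existing rows. Add, by arm and study phase, the number and percentage of patients with:

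- any post-baseline central-laboratory potassium above 5.5 mEq/L;
- any post-baseline central-laboratory potassium of 6.0 mEq/L or more;
- any post-baseline visit systolic pressure below 90 mmHg, without the fall condition.

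These levels already stand in the documents. By construction the new rows have no unflagged band at those levels. Label the potassium rows as programmed from laboratory values and show them beside the AESI count rather than in place of it, because unscheduled samples may go to a local laboratory (Protocol 8.4.1).

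**Protocol.** The potassium alert range in Appendix 1, as used in 8.4.1 and 10.1.1, and the absolute bands in Appendix 2 should be reconciled by the sponsor's clinical team. No clinical rule is proposed here.

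**Cost.** Three extra descriptive rows from data already collected, and one protocol clarification. No new samples or visits. The downside is slightly longer tables.
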